2.7.2. Hypoglycemic Events

The proportion (percentage) of patients affected by hypoglycemia will be reported by treatment regimen. The hypoglycemic information will come from the data entered in the Hypoglycemic / Hyperglycemic log.

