1.3.2 Secondary Objectives

The secondary objectives of this study are:

1. To compare the change from baseline in number of hypoglycemic episodes in subjects treated with Oral Insulin dosed QD to Oral insulin dosed TID in subjects with T1D over the last 10 days of each treatment period.
2. To compare the change from baseline in HbA1c levels in subjects with T1D treated with Oral Insulin dosed QD or Oral Insulin dosed TID as measured at the end of each treatment period.
3. To explore differences in glucodynamic between the different dosing regimens during the last 10 days of each treatment period.
4. To evaluate the safety of Oral Insulin through the recording of adverse events, clinical laboratory tests results (hematology, chemistry and urinalysis) and vital signs.

2. Detailed Statistical Methods

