2.1. General Statistical Methods

All measured variables and derived parameters will be listed individually and, if appropriate, tabulated by descriptive statistics. For descriptive statistics summary tables will include by study group summaries of sample size, arithmetic mean, standard deviation, median, minimum and maximum values, and 95% Confidence Intervals (if appropriate). For categorical variables summary tables will include by study group summaries of frequency counts.

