2.8. Efficacy Evaluations

The primary endpoints for the study are:

1. To compare the amount of basal, bolus and total (basal + bolus) exogenous insulin utilized over the final 10 days of each treatment period.
2. To compare the impact of Oral Insulin dosed QD to Oral Insulin dosed TID and associated adjustments of basal and bolus insulin on mean 24-hour CGM glucose levels during the final 10 days of each treatment period.

The secondary endpoints for the study are:

1. Glucodynamics over the final 10 days of each treatment period as measured by CGM:
 - a. Time in range 70 – 180 mg/dL
 - b. Time <70 mg/dL
 - c. Time >180 mg/dL
 - d. Time >250 mg/dL
 - e. Glucose Coefficient of Variation
 - f. Low Blood Glucose Index (LBGI)
 - g. Glucose below 70 mg/dL Area Over the Curve (AOC₇₀)
2. Total daily non-oral insulin requirements in units per kilogram (kg) body weight over the last 10 days of each treatment period.

The exploratory endpoints for the study are:

1. HbA1c measured at the end of each treatment period
2. Patient diary-reported carbohydrate intake over the final 10 days of each treatment period
3. Changes in body weight from baseline (Visit 3) to the end of each treatment period
4. Other measures of hypoglycemia
 - a. Severe hypoglycemia events (impaired or loss of consciousness requiring assistance of another)
 - b. Documented symptomatic hypoglycemia (an event during which typical symptoms of hypoglycemia are accompanied by a measured plasma glucose concentration <70 mg/dL)
 - c. Total time <70 mg/dL by CGM
 - d. Nocturnal hypoglycemia, severe or documented symptomatic episodes (as defined above) occurring after the subject has retired for the primary sleeping period.

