2.8.1. Statistical Considerations

Subjects will be analyzed under 3 treatment regimens: Standard of Care (Baseline), Once a Day Dosing (QD) and Three Times a Day Dosing (TID).

Information collected in the daily diaries or via the Continuous Glucose Monitor (CGM) on the final 10 days of treatment will be analyzed using a Repeated Measures Analysis of Covariance with subject as a random effect with each of the 10 days being a single measurement. When analyzing the exogenous insulin variables, the CGM parameters (mean 24 hour glucose value and 24 hour time within 70-180 mg/dL range) and the patient reported carbohydrate intake will be included as covariates. When analyzing CGM parameters, the exogenous insulin (basal and bolus insulin amounts) and patient reported carbohydrate intake will be included as covariates. Treatment least squares means and change from baseline estimates will be derived using this linear model.

Information collected at the day 28 visits (Day 28 and Day 56) will be analyzed using an Analysis of Covariance model with subject as a random effect. Treatment least squares means and change from baseline estimates will be derived using this linear model.

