2.8.3. Continuous Glucose Monitoring

Continuous Glucose Monitoring (CGM) will be summarized using 3 different time intervals:

- Daytime (6AM to 10PM),
- Nighttime (10PM to 6AM) and
- 24 Hour (6AM to 6AM).

The area under the curve (AUC) will be derived for each of the time periods for each of the 10 days for each treatment regimen. The average glucose measurement will be derived by dividing the AUC by the number of observed hours.

In addition to the mean values, the following CGM parameters will be derived for each time interval:

- Time that Glucose Value is Between 70 and 180,
- Time that Glucose Value is Less Than 70,
- Time that Glucose Value is Greater Than 180,

- Time that Glucose Value is Greater Than 250,
- Low Blood Glucose Index, and
- Glucose below 70 mg/dL Area Over the Curve (AOC₇₀)

All of the CGM parameters will be analyzed for each of the time periods (24-hour, daytime and nighttime) using the Repeated Measures Analysis of Covariance Model indicated in section 2.8.1.

Individual and mean figures will be generated to present the glucose curves / data for the 24-hour, daytime and nighttime measurements.

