2.8.4. Other Endpoints of Interest

HbA1c, average patient reported carbohydrate intake and body weight will be summarized using an Analysis of Covariance Model as indicated in Section 2.8.1.

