2.10. Other Analyses

No other analyses are planned at this time.

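### Secondary objective 1 is about the number of hypoglycemic episodes, but the SAP's dedicated analysis gives only the percentage of patients affected, with no count and no QD–TID contrast

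*SAP*

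**What the plan says.** The objective is the same in Protocol 2.1.2 and SAP 1.3.2: "To compare the change from baseline in number of hypoglycemic episodes" between QD and TID, over the final 10 days of each treatment period.

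The matching analysis section is SAP 2.7.2: "The proportion (percentage) of patients affected by hypoglycemia will be reported by treatment regimen". It takes its data from a hypoglycemic/hyperglycemic log.

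Other places bear on the point:

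- SAP 2.1 is general: "All measured variables and derived parameters will be listed individually and, if appropriate, tabulated by descriptive statistics".
- SAP 2.8.1 defines three regimens, one of them Baseline, and gives the repeated-measures model its scope: "Information collected in the daily diaries or via the Continuous Glucose Monitor (CGM) on the final 10 days of treatment will be analyzed".
- SAP 2.8.2 covers insulin. SAP 2.8.3 covers CGM: "All of the CGM parameters will be analyzed for each of the time periods". SAP 2.8.4 covers three more variables: "HbA1c, average patient reported carbohydrate intake and body weight will be summarized using an Analysis of Covariance Model".
- SAP 2.10 closes the list: "No other analyses are planned at this time".
- Severe, documented symptomatic and nocturnal episodes are defined as exploratory endpoints (Protocol Synopsis and 2.2; SAP 2.8). The Synopsis gives them the 10-day window. No analysis method is attached to them.
- Table 14.3.4 summarises hypoglycemic events, but SAP 4.5 puts the shells in a separate file.

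**The concern.** The objective's quantity is a number of episodes, compared within subject and against baseline. The stated analysis is a proportion of patients, by regimen. The two can move independently: ten patients with one episode each and ten patients with three each give the same percentage, although the counts are 10 and 30.

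If the SAP is followed as written, secondary objective 1 has no stated estimate. The definition, the count and the contrast would then be chosen once data are available, in an open-label study.

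**Working it through.** **Objective against plan.** There is no figure in the plan to reproduce, because no event rate, alpha or power is given for this objective.

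| Element of objective 1 | SAP 2.7.2 | Elsewhere |
|---|---|---|
| Number of episodes | Percentage of patients | No count stated; TEAE tables (SAP 2.7.1; Protocol 8.6.2) are subject-level incidence |
| Change from baseline | Not stated | Baseline may appear as a regimen (SAP 2.8.1), as a percentage |
| QD–TID contrast | Not stated | Stated for insulin (2.8.2); none for episodes |
| Last 10 days | Not repeated | Given in SAP 1.3.2 and the Protocol Synopsis |
| Episode definition | Not named | Several defined; none assigned to objective 1 |

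The seven efficacy tables (14.2.1, 14.2.2.1 to 14.2.2.3, 14.2.3 to 14.2.5) cover insulin, CGM, carbohydrate, HbA1c and weight. None is on episodes.

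**What a percentage leaves out.** All rates here are assumptions. For r episodes per week, the mean per 10 days is m = 10r/7. The chance of at least one episode is P = 1 − exp(−m) for Poisson counts, or P = 1 − (1 + m/k)^(−k) when subjects vary with gamma shape k. The share of episodes that are repeats within a patient is 1 − P/m.

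| r per week | m | % affected: Poisson / k=2 / k=1 | % repeats: Poisson / k=2 / k=1 |
|---|---|---|---|
| 0.5 | 0.714 | 51.0 / 45.7 / 41.7 | 28.5 / 36.0 / 41.7 |
| 1 | 1.429 | 76.0 / 66.0 / 58.8 | 46.8 / 53.8 / 58.8 |
| 2 | 2.857 | 94.3 / 83.0 / 74.1 | 67.0 / 70.9 / 74.1 |
| 4 | 5.714 | 99.7 / 93.3 / 85.1 | 82.6 / 83.7 / 85.1 |

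A simulation of 26 paired subjects (k=2, rate doubled, no period effect or dropout, two-sided 0.05) compared a paired t-test on counts with an exact McNemar test on any-episode status. Power was 48% against 22% at 0.5 versus 1 episode per 10 days, and 79% against 27% at 1 versus 2. The plan specifies neither test. The figures show only the direction of the loss under these assumptions.

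**What can be estimated.** For a subject with both active periods, (QD − baseline) − (TID − baseline) = QD − TID, so the contrast needs no baseline count. Change from baseline is different. The run-in always comes first, so a model with three regimens and three period levels has 5 columns but rank 4. QD − TID is estimable there. QD minus run-in and TID minus run-in are not separable from time.

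**Precision of a count analysis.** With n = 24, expected episodes per regimen are 24m = 17.1, 34.3 and 68.6 at 0.5, 1 and 2 per week. For a Poisson rate ratio within subject, the 95% CI factor is about exp(1.96 × √(2/(24m))) = 1.95, 1.60 and 1.40. Simulation with k=2 and a period effect gave 2.00, 1.62 and 1.41. Added subject-by-period overdispersion widened these to about 2.3–2.4, 1.9–2.0 and 1.7–1.8.

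**Observed days.** The ±2-day windows allow (28 − 2) − (18 + 2) = 6 to (28 + 2) − (18 − 2) = 14 days between Visits 4 and 5. The same holds for Visits 6 and 7. These are extremes, since subjects are told to return after 10 days, and no passage ties the log to these visits.

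**The case against.** The strongest defence is that the plan contains more on hypoglycemia than 2.7.2.

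- Protocol 7.3.1 grades hypoglycemia as an adverse event, so it can also reach the TEAE tables and the AE listing. A reader might infer that repeat episodes would be visible only in the log listing. The documents do not support that, and the unseen Table 14.3.4 shell might show counts. What stands is that the TEAE tables count subjects and the SAP text defines no count.
- By-regimen reporting may include Baseline, so three percentages could stand side by side. That is still not a change in number.
- Protocol 5.5 says that compliance is also recorded in the diary, so the diary's described content (insulin and carbohydrate) is not complete. If the log is part of the diary, the model in SAP 2.8.1 might reach it. No passage says that it is, and 2.8.2 to 2.8.4 name no episode outcome.
- A reader might infer that no episode definition exists. Several do; what is missing is the assignment of one to objective 1.
- Time below 70 mg/dL, LBGI and AOC70 are modelled, so exposure to low glucose is covered. These are related measures, not episode counts.
- This is an unpowered Phase 2 study. That limits what a count analysis can show, but the SAP still specifies estimates with 95% CIs for insulin without a power calculation.

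**Conclusion.** The mismatch holds on the text: the dedicated analysis does not estimate the quantity in secondary objective 1, and no other passage supplies the count or the contrast. It should be fixed before analysis.

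Its size cannot be fixed from the documents. Over assumed rates of 0.5 to 2 episodes per week, repeats make up 29% to 74% of episodes. A reader might infer that the percentage is either nearly uninformative or nearly adequate. Neither follows, because that depends on the rate and on variation between subjects: with k=2, the percentage affected runs from 46% at 0.5 per week to 93% at 4 per week.

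The conclusion is limited to the SAP text, since the table shells were not seen. It also does not require one particular model. A paired difference in counts is closest to the objective's wording, and a rate model is an equally reasonable choice.

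**What to change.** First confirm that the log covers the final 10 days of each active period (and the run-in), and that it records what the chosen definition needs, such as glucose value, symptoms and timing. Then, in SAP 2.7.2:

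1. Name one existing protocol definition for objective 1, for example documented symptomatic hypoglycemia below 70 mg/dL.
2. Report the number of episodes per subject over the final 10 days of the QD and TID periods, standardised to observed days.
3. Estimate the within-subject QD–TID contrast with a 95% CI, allowing for period. Either take the paired difference in counts, averaged within each sequence and then across the two sequences, or take a rate ratio from a Poisson or negative-binomial model with regimen, period and subject effects and a log observed-days offset.
4. If the log was kept during run-in, report change from run-in by regimen on the same window and state that it is confounded with time. If it was not, state that change from baseline cannot be estimated.
5. Keep the percentage affected as a supportive display, and summarise severe and nocturnal events descriptively.

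The cost is one SAP paragraph and a matching shell for Table 14.3.4, using a log already planned for listing. The downside is a little more analysis work and an estimate that will be imprecise and unpowered at about 24–26 subjects.

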2.7.3. Safety Laboratory Evaluations

Screening, pre-dose values (Day 1 of treatment), post-dose values (Day 28 of treatment) and change from pre-dose to post-dose will be described using summary statistics for each parameter for each treatment regimen. All laboratory results will be presented in listings.

A clinically significant abnormal value or clinically significant change from baseline (Screening), may be recorded as an AE, if deemed appropriate by the PI or sponsor.

2.7.4. Vital Signs

Screening, pre-dose values (Day 1 of treatment), Day 18 of treatment, Day 28 of treatment and change from pre-dose to Days 18 and 28 will be described using summary statistics for each parameter for each treatment regimen. All vital sign results will be presented in listings.

A clinically significant change from baseline may be recorded as an AE, if deemed appropriate by the PI or sponsor.

2.7.5. Electrocardiogram

ECG was collected at screening only. All ECG results will be presented in listings.

2.7.6. Physical Examination

The Screening and end of study results will be described using frequency counts for each body system.

All physical exam findings will be presented in the data listings.

2.8. Efficacy Evaluations

The primary endpoints for the study are:

1. To compare the amount of basal, bolus and total (basal + bolus) exogenous insulin utilized over the final 10 days of each treatment period.
2. To compare the impact of Oral Insulin dosed QD to Oral Insulin dosed TID and associated adjustments of basal and bolus insulin on mean 24-hour CGM glucose levels during the final 10 days of each treatment period.

The secondary endpoints for the study are:

1. Glucodynamics over the final 10 days of each treatment period as measured by CGM:
 - a. Time in range 70 – 180 mg/dL
 - b. Time <70 mg/dL
 - c. Time >180 mg/dL
 - d. Time >250 mg/dL
 - e. Glucose Coefficient of Variation
 - f. Low Blood Glucose Index (LBGI)
 - g. Glucose below 70 mg/dL Area Over the Curve (AOC₇₀)
2. Total daily non-oral insulin requirements in units per kilogram (kg) body weight over the last 10 days of each treatment period.

The exploratory endpoints for the study are:

1. HbA1c measured at the end of each treatment period
2. Patient diary-reported carbohydrate intake over the final 10 days of each treatment period
3. Changes in body weight from baseline (Visit 3) to the end of each treatment period
4. Other measures of hypoglycemia
 - a. Severe hypoglycemia events (impaired or loss of consciousness requiring assistance of another)
 - b. Documented symptomatic hypoglycemia (an event during which typical symptoms of hypoglycemia are accompanied by a measured plasma glucose concentration <70 mg/dL)
 - c. Total time <70 mg/dL by CGM
 - d. Nocturnal hypoglycemia, severe or documented symptomatic episodes (as defined above) occurring after the subject has retired for the primary sleeping period.

2.8.1. Statistical Considerations

Subjects will be analyzed under 3 treatment regimens: Standard of Care (Baseline), Once a Day Dosing (QD) and Three Times a Day Dosing (TID).

Information collected in the daily diaries or via the Continuous Glucose Monitor (CGM) on the final 10 days of treatment will be analyzed using a Repeated Measures Analysis of Covariance with subject as a random effect with each of the 10 days being a single measurement. When analyzing the exogenous insulin variables, the CGM parameters (mean 24 hour glucose value and 24 hour time within 70-180 mg/dL range) and the patient reported carbohydrate intake will be included as covariates. When analyzing CGM parameters, the exogenous insulin (basal and bolus insulin amounts) and patient reported carbohydrate intake will be included as covariates. Treatment least squares means and change from baseline estimates will be derived using this linear model.

Information collected at the day 28 visits (Day 28 and Day 56) will be analyzed using an Analysis of Covariance model with subject as a random effect. Treatment least squares means and change from baseline estimates will be derived using this linear model.

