### **3.4 Visit 3 (Day 1 ± 2 days)**

Subjects will report to the CRU in the morning in fasting state. The following procedures will be performed:

- Collect data from CGM monitor;
- Review of medications and supplements;
- Collect and review diary;
- Measurement of vital signs (weight, seated SBP/DBP, and heart rate);
- Urine pregnancy Test for women of childbearing potential
- Collect fasting blood samples for serum chemistry (with fasting plasma glucose/FPG) and HbA1c;
- Review inclusion and exclusion criteria.
- Randomization of subjects to their individual study treatment sequence;
- Dispensing of IMP and instructions on use of IMP.
- Adverse events will be monitored and recorded.

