#### **4.3 Subject and Trial Discontinuation**

Subjects may choose to withdraw from this study at any time for any reason without penalty of jeopardizing their health care or loss of benefits to which the subject is otherwise entitled.

Within the provisions of informed consent and good clinical judgment with respect to safety, every attempt will be made to have subjects complete the study. The following are reasons to terminate a subject's participation in the study:

1. Subject experiences an AE that in the judgement of the Investigator poses a significant risk to the subject for continued participation in the study.
  - a. If a subject experiences hyperglycemia, defined in Section 7.3.2, blood glucose will be checked 1-2 hours later. If the glucose remains elevated, the subject will be withdrawn from the study.
2. Subject uses a prohibited medication (listed in Section 5.7) that in the judgment of the Investigator poses a significant risk to the subject for continued participation in the study or that will interfere with the interpretation of the results of the study.
3. Subject becomes pregnant.
4. Significant protocol violation or noncompliance on the part of the subject or the Investigator.
5. Intercurrent illness that requires treatment that is not consistent with the protocol requirements, or intercurrent illness or the associated treatment that in the judgment of the Investigator poses a significant risk to the subject for continued participation in the study.
6. Subject wishes to withdraw for any reason.
7. Sponsor elects to end the study, or the Investigational Site elects to end the study at their site.
8. Any other reason that in the judgment of the Investigator poses unacceptable risk to the subject.

Reasons for study drug discontinuation may include the following:

1. Adverse event
2. Episodes of hypoglycemia as defined in Section 7.3.1.
3. Subject meets one of the exclusion criteria during the study
4. Any clinically significant change in the subject's medical condition

Subjects who withdraw from the study prior to treatment may be replaced. Subjects who are withdrawn and have received at least one treatment will not be replaced. Subjects who discontinue study drug treatment will not be replaced.

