## **5.2 Randomization**

This is a randomized, open label, crossover study. Approximately 26 eligible subjects with T1D will be randomized to all 2 treatment schedules.

Integrium, LLC will generate and implement the randomization procedures for this trial. A computer-generated randomization schedule will be used for assigning treatment schedules. The Investigational Site pharmacist will follow this randomization schedule to dispense the appropriate study treatment.

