### 8.2 Statistical Considerations

Subjects will be analyzed under 3 treatment regimens: Standard of Care (Baseline), Once a Day Dosing (QD) and Three Times a Day Dosing (TID).

Information collected in the daily diaries or via the Continuous Glucose Monitor (CGM) on the final 10 days of treatment will be analyzed using a Repeated Measures Analysis of Covariance with subject as a random effect with each of the 10 days being a single measure. When analyzing the exogenous insulin variables, CGM parameters (mean 24 hour glucose value and 24 hour time within 70-180 mg/dL range) and patient reported carbohydrate intake will be included as covariates. When analyzing CGM parameters, exogenous insulin (basal and bolus insulin amounts) and patient reported carbohydrate intake will be included as covariates. Treatment least squares means and change from baseline estimates will be derived using this linear model.

Information collected at the day 28 visits will be analyzed using an Analysis of Covariance model with subject as a random effect. Treatment least squares means and change from baseline estimates will be derived using this linear model.

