2.5. Study Drug Duration and Compliance

This is a two-period crossover study. A table summarizing the number of days on study medication, the number of tablets taken and the percent compliance (100*number of tablets taken / expected number of tablets) by treatment regimen will be presented.

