2.12. Randomization Scheme and Codes

The randomization details for this study are presented in a separate randomization plan.

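### No period term is specified for the two-period crossover, so a period effect can enter QD-minus-TID through sequence imbalance or, even at exact balance, through the planned concurrent covariates

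*SAP*

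**What the plan says.** SAP 2.5 describes the design plainly: "This is a two-period crossover study". Protocol 3.4 lists, at Visit 3, "Randomization of subjects to their individual study treatment sequence".

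The analysis model carries none of that structure. SAP 2.8.1 defines the comparison factor: "Subjects will be analyzed under 3 treatment regimens: Standard of Care (Baseline), Once a Day Dosing (QD) and Three Times a Day Dosing (TID". For diary and CGM data, Protocol 8.2 (and the SAP in near-identical words) plans a "Repeated Measures Analysis of Covariance with subject as a random effect with each of the 10 days being a single measure". Insulin endpoints are adjusted for mean 24-hour glucose, time in range and carbohydrate intake. CGM endpoints are adjusted for basal insulin, bolus insulin and carbohydrate intake. The visit endpoints follow the same section: "HbA1c, average patient reported carbohydrate intake and body weight will be summarized using an Analysis of Covariance Model as indicated in Section 2.8.1". Neither document names a period or sequence term anywhere.

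On balance, Protocol 5.2 says "A computer-generated randomization schedule will be used for assigning treatment schedules", and SAP 2.12 adds "The randomization details for this study are presented in a separate randomization plan". Protocol 4.3 says "Subjects who are withdrawn and have received at least one treatment will not be replaced". The same section lets withdrawals before treatment be replaced, yet later rules out replacing any randomised subject who discontinues. SAP 2.3 tabulates disposition overall, and no table title in SAP 4.1 mentions sequence.

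**The concern.** Both primary endpoints are read in Days 18–28 and again in Days 46–56, 28 days apart. Insulin dose is adjusted by the subjects themselves (Protocol 3.1), so some drift between the windows is plausible whatever the regimen. A crossover analysis normally separates that drift from treatment with a period term. Without one, part of the drift can be attributed to QD versus TID. The trial is open label, so adding the term once data have been seen would be a post-hoc model choice.

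**Working it through.** **Inputs.** The model is from SAP 2.8.1 and Protocol 8.2. Planned size conflicts: 24 randomised (Protocol 8.1), about 26 randomised (SAP 2.11), about 26 completers (synopsis). I use 26 for bias and 24 for the one-value endpoints; the choice does not alter the conclusion. The period effect π (period 2 minus period 1), the variances and the allocation ratio are not given. Allocation of 1:1 and every imbalance, loss pattern and covariate shift below are assumptions. There is no plan figure to reproduce.

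**1. Complete data, covariates ignored.** A QD-first subject's QD-minus-TID difference has expectation τ − π; a TID-first subject's has τ + π. Averaging:

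E[QD − TID] = τ + π × (n_TID-first − n_QD-first)/n

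- 13/13: 0
- 14/12: 2/26 = 0.077 of π (absolute value)
- 13/11: 2/24 = 0.083
- 15/11: 4/26 = 0.154

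Let r = π/SD_d, where SD_d is the SD of the within-subject difference. At 14/12 the bias in standard errors is 0.077 × r × √26, which is 0.10, 0.20 and 0.29 for assumed r of 0.25, 0.5 and 0.75.

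**2. Losses after period 1 from 13/13, covariates ignored.** Generalised least squares was used with three regimens × 10 days, a random subject intercept, and a subject-to-day variance ratio of 0.25–4.

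- one loss: 0.03
- four split 2:2: 0
- four split 3:1: 0.06–0.07
- three one-sided: 0.09–0.10
- four one-sided: 0.13–0.14 (completers alone would give 4/22 = 0.18; the model recovers some information from those lost)

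If losses fall at random, all three land in one sequence with probability 2 × 286/2600 = 22%, and all four with 2 × 715/14950 = 10%.

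**3. Exact 13/13 balance, covariates included.** Take k independent covariates, each shifted by a day-SDs under QD and by b day-SDs in period 2. Code period 0 at run-in, −0.5 in period 1 and +0.5 in period 2. Per subject, this code has sum of squares 10 × (0.25 + 0.25) = 5. Each covariate's within-subject noise is about 29 (30 days less the subject mean). With no period term, the covariates stand in for period, and the share of the direct period effect entering QD-minus-TID is

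5kab/(29 + 5kb²)

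| k | a = b = 0.5 | a = b = 1 |
|---|---|---|
| 1 | 1.25/30.25 = 0.04 | 5/34 = 0.15 |
| 3 | 3.75/32.75 = 0.11 | 15/44 = 0.34 |

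A separate simulation of the k = 1, a = b = 1 case gave 0.154. If the covariates do not respond to regimen (a = 0), the leakage at balance is zero. The sign follows the signs of a and b, so this route can add to or offset step 1.

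**4. With the indicator.** The bias was 0.000 in every case under steps 1 and 2. In the simulation for step 3 it was −0.006, which is zero within simulation error. The standard-error cost when π = 0:

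- no covariates: 0% if balanced; 1/√(1 − 0.077²) = 1.003 at 14/12; 0.84–0.94% for four one-sided losses
- k = 3, a = b = 1, 13/13: √[(0.2 + 3/29)/(0.2 + 3/44)] = √(0.303/0.268), about 6%
- k = 3, a = b = 1, 14/12, in the less favourable direction: without the term 0.2 + 3 × 0.923²/43.9 = 0.258; with it 0.2/(1 − 0.077²) + 3/29 = 0.305; about 9%

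**5. One-value endpoints (HbA1c, average carbohydrate, weight), n = 24, balanced.** The omitted period effect adds 24r² residual variances to the error sum of squares. The interval therefore widens by √[(df + 24r²)/df] × t_df/t_(df−1). SAP 2.8.1 does not settle whether baseline is a third record per subject (df = 72 − 24 − 2 = 46) or only Days 28 and 56 enter (df = 48 − 24 − 1 = 23).

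| r | 46 df | 23 df |
|---|---|---|
| 0.25 | 2% | 3% |
| 0.5 | 6% | 12% |
| 0.75 | 14% | 26% |

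**The case against.** The best defence is that a balanced crossover cancels period by design, and that the separate randomisation plan may well block the sequences. This is also an unpowered study reporting estimates with 95% intervals, and at 14/12 the bias without covariates is at most 0.29 standard errors over the assumed range.

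Much of that stands. With complete, balanced data and no covariates the bias is zero. The allocation plan cannot be seen, and nothing in the documents shows that blocking is absent. The size of any period effect is unknown.

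Two parts do not stand. Balance at randomisation does not secure balance among those analysed, because discontinued randomised subjects are not replaced. And balance is not enough for the primary models as written, because covariates that respond to both regimen and period carry the effect through at 13/13. The reliance on SAS defaults in SAP 2.15 does not help, since no default adds a period effect.

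A reader might go further and infer that QD-minus-TID will be biased. The documents do not support that: they give no period effect, no realised imbalance and no covariate shifts.

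**Conclusion.** The point holds. The plan leaves out a standard term, and an additive period effect can enter the main contrast through imbalance or through the concurrent covariates. Leakage is a fraction of an unknown quantity: zero in the most favourable case, about 0.08–0.14 for modest imbalance without covariates, and up to about a third at exact balance if three independent covariates shift strongly in the same direction. That upper figure is an extreme. Mean glucose and time in range are unlikely to act as independent covariates, and opposing shifts would partly cancel. The term should be added before analysis, but its absence does not by itself invalidate the comparison.

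It would also be wrong to infer that a period term settles every time-related problem. An assumed QD carry-over of 1 unit biased QD-minus-TID by about 0.49 with or without it. Run-in always comes first, so changes from baseline remain mixed with time.

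**What to change.** In SAP 2.8.1, add one fixed indicator of period 2 versus period 1 to both the repeated-measures model and the Day 28/56 ANCOVA. Code it neutrally for run-in rows, for example 0 at baseline, −0.5 in period 1 and +0.5 in period 2, so that regimen means and changes from baseline refer to the average of the two periods. Do not use a three-level period factor: it is aliased with the Baseline regimen, and the baseline mean and changes from it would no longer be estimable. State whether baseline enters the ANCOVA as a record. Report numbers randomised and analysed per sequence in the disposition table, which otherwise have to be rebuilt from listings 16.1.7 and 16.2.1. Reconcile the planned sample size and the replacement statements in Protocol 4.3.

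The cost is 1 df. If there is no period effect, the standard error rises by 0% when balanced, 0.3% at 14/12 and under 1% with four one-sided losses, all without covariates. It rises by roughly 6–9% if three covariates shift by 1 day-SD with both regimen and period, and by more under heavier imbalance. No new data are needed.
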